**Clinical Study Protocol Synopsis**

Title	The Evalua T ion of the Safety and E fficacy of Sustai N ed Release D examethasone Intra c analicular In s ert (DEXTENZA) in p E diatric patients following R etinal surgery or laser treatment under anesthesia
Site Location(s)	Duke University Eye Center
Principal Investigator	[name]
Objective(s)	To determine safety and efficacy of the dexamethasone ophthalmic insert in pediatric patients following retinal surgery or laser treatment under anesthesia
Study Design	Prospective Open-label Interventional Study
Study Duration	45 days postoperative
Estimated Study Completion Date	August 1, 2023
Population	
Sample Size:	30
Target Population:	Pediatric patients ages 3 to 17 undergoing routine retinal surgeries or laser treatment under anesthesia
Study Drug	DEXTENA (dexamethasone ophthalmic insert) 0.4 mg, for intracanalicular use
Dose/Route/Schedule:	
All eyes will undergo routine retinal surgery or laser treatment under anesthesia.
 
Patients in each treatment group (surgery or laser) will be randomized 2:1 at the time of surgery/laser to either:
 
 
1) Treatment Arm: Dextenza insert intraoperatively for perioperative ocular inflammation and pain. These patients will not be prescribed topical
 

steroid drops post-operatively, or

- 2) Control Arm: Prednisolone forte 1% steroid drop taper for 28 days post-operatively to treat perioperative ocular inflammation and pain; drops four times per day (QID) on days 0-7, three times per day (TID) on days 7-14, twice per day (BID) on days 14-21 and once per day (QD) on days 21-28.

Each treatment group (surgery or laser) will include 15 patients total, 10 receiving Dextenza and 5 receiving the control drug.

Drops for dilation and antibiotic coverage will be used as clinically indicated in all groups and arms.

There will be a total of six visits for both treatment arms Screening/Baseline visit (day -30 to 0), Surgical Visit (day 0), and four post-operative follow up appointments occurring at post-op day 1, 7, 28/30 and 45 ( +/- three days for all post-operative timepoints). Exams to be performed on these days are outlined in section 5.1.. Treatment Arm Schedule of Events in Table 1. Control Arm Schedule of Events in Table 2

---

## Endpoint(s)

### Primary Endpoint:

To evaluate if pediatric patients receiving retinal surgery or laser would benefit from DEXTENZA implant compared to topical ocular drop therapy to manage post-operative pain (measured with the Face, Legs, Activity, Cry Consolability (FLACC) Behavioral Pain Rating Scale). Pain will be measured at each visit with final outcome determined by the FLACC Pain Rating Scale score on day 45 (final visit).

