##### **4.1.1 Inclusion Criteria**

A patient's study eye must meet the following criteria to be eligible for inclusion in the study:

- 3 to <17 year old pediatric patients undergoing routine retinal surgery or laser treatment under anesthesia for a variety of visual conditions. These conditions and procedures include but are not limited to:
  - Conditions:
    - Familial Exudative Vitreoretinopathy
    - Coats' Disease
    - Exudative Retinopathy
    - Lattice degeneration
    - Retinal holes
    - Sickler's syndrome
    - Retinal detachment, rhegmatogenous
    - Retinal detachment, exudative
    - Retinal detachment, tractional
  - Procedures
    - Laser photocoagulation
    - Cryotherapy
    - Retinal detachment repair with scleral buckle and cryotherapy
    - Retinal detachment repair with vitrectomy
- Written informed consent from parent/legal guardian

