##### **Preprocedural**

- Subjects needing laser or ocular surgery in the fellow eye concurrently as the study eye.
- Active or history of chronic or recurrent inflammatory eye disease in either eye
- Any patient of reproductive potential that has a positive pregnancy test during pre-procedural testing
- Active or history of increased ocular pressure
- Patients with active corneal, conjunctival, and canalicular infections
- Patients with punctal stenosis or other punctal anatomical abnormalities that would not be conducive with device insertion
- Nasolacrimal duct obstruction
- Laser or incisional ocular surgery during the study period and 3 months prior in the study eye
- current use of systemic or topical steroids or NSAIDS on a regular basis

- History of autoimmune disease that may interfere with treatment/outcomes
- Ocular pain at the time of screening
- Known malignancy
- Current use of cyclosporin or a TNF blocker
- Ocular hypertension IOP >25, actively taking medications for ocular hypertension, any history of IOP spikes in either including steroid associated IOP elevation
- Congenital ocular lid and tear duct system abnormalities (e.g. congenital ectropion/entropion, trichiasis)
- Evidence of acute external ocular infection of the study eye
- Active or history of HSV
- Previous trauma causing deformity
- Previous enrollment or current enrollment with another clinical trial within the last 30 days that may interfere with treatment
- Known allergies to product under investigation
- Inability to engage in VA testing
- Investigator determines that the candidate is not eligible for participation based on clinical or historical factors that would interfere with treatment or impact patient safety not specified above
- Current artificial tear use >4x daily
- Anyone who, in the opinion of the investigator, would not be a good candidate for the study.

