## **5.2 Study Visit Descriptions for control and treatment arms**

### **5.2.1 Study Procedures**

#### **Visit 1 (Day -30 to 0) Screening/Baseline**

After the patient has provided informed consent, the following information will be collected:

- Inclusion/exclusion
- Demographics
- Medical history and concurrent illnesses
- Concomitant medications
- Subject reported AE's prior to surgery
- Ocular Pain Assessment (FLACC)
- Distance VA testing, when applicable
- Best-corrected visual acuity as measured by ETDRS or HOTV chart at 4m based on patient age (HOTV for pre-literate patients)
- Anterior chamber cell count
- Anterior chamber cell flare
- Punctum examination
- Intraocular pressure
- Ophthalmic Examination including dilated fundus exam

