**10.3 FLACC Pain Rating Scale for measuring ocular pain**

The FLACC Scale will be used in the assessment of pain. BCVA and FLACC will occur prior to other visit assessments. The FLACC assessment will be performed by masked site personnel.

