## **FLACC scale**

**Behavioral Observation Pain Rating Scale**

Categories	Scoring		
	0	1	2
Face	No particular expression or smile; disinterested	Occasional grimace or frown, withdrawn	Frequent to constant frown, clenched jaw, quivering chin
Legs	No position or relaxed	Uneasy, restless, tense	Kicking, or legs drawn up
Activity	Lying quietly, normal position, moves easily	Squirming, shifting back and forth, tense	Arched, rigid, or jerking
Cry	No crying (awake or asleep)	Moans or whimpers, occasional complaint	Crying steadily, screams or sobs, frequent complaints
Consolability	Content, relaxed	Reassured by occasional touching, hugging, or talking to. Distractable	Difficult to console or comfort
Each of the five categories (F) Face; (L) Legs; (A) Activity; (C) Cry; (C) Consolability is scored from 0-2, which results in a total score between 0 and 10.			

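### The primary pain outcome is the unadjusted day-45 FLACC score; FLACC is also scored at screening, but no use of that score in the pain analysis is specified

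*Combined protocol and SAP*

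**What the plan says.** The Primary Endpoint in the synopsis reads: "Pain will be measured at each visit with final outcome determined by the FLACC Pain Rating Scale score on day 45 (final visit". Section 2.1 says the same. Neither mentions change from baseline or adjustment for it.

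A baseline value exists. Section 5.2.1 lists "Ocular Pain Assessment (FLACC" among the Visit 1 procedures, and Tables 1 and 2 mark it at Screening/Baseline for both arms. Section 4.1.2 excludes children with "Ocular pain at the time of screening", without saying how that is judged.

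The scale in Appendix 10.3 has five observed-behaviour categories. One Activity descriptor is "Squirming, shifting back and forth, tense"; other categories cover crying and consolability. Each category "is scored from 0-2, which results in a total score between 0 and 10". Entry begins at age 3: "3 to <17 year old pediatric patients undergoing routine retinal surgery or laser treatment under anesthesia".

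Section 8.1 plans descriptive summaries by arm, overall and by procedure group, and does not name FLACC. Section 8.1.1 will summarise selected pre-treatment clinical variables, also without naming FLACC. In Section 2.2, BCVA is analysed as change from baseline. Resolution of inflammation has a threshold there; resolution of pain has none.

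**The concern.** The FLACC items can be scored in a young child who is upset for reasons other than eye pain. The documents do not say this outright; it is an inference from the item wording. Because ocular pain at screening is an exclusion, a screening score above 0 in an enrolled child should not, by the protocol's own rule, be ocular pain. The trial therefore collects some information on each child's other behaviour and then plans no use of it when reading the post-operative scores.

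Two things are at stake. First, a non-zero day-45 score may be read as persisting pain when the child had the same score before the procedure. This affects absolute results in either arm, whatever randomisation does. Second, the arms are small and results will be shown by procedure group, so a few such children falling in one arm can look like a treatment difference in pain.

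**Working it through.** **Inputs from the documents.** Allocation is 2:1 within two procedure groups of 15 (Section 4.1). 15 × 2/3 = 10 and 15 × 1/3 = 5 per group; doubled, this is 20 and 10, total 30, which matches the plan. There is no power calculation to reproduce: Section 8.1 says that the sample size is not designed to give power.

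**Inputs assumed.** The documents give neither the SD of FLACC, nor the correlation ρ between screening and day-45 scores, nor the share of children scoring above 0 without ocular pain. I express standard errors in SD units, take ρ from 0.2 to 0.8 with equal SDs at the two visits, and take the share from 10% to 50%.

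**Step 1: what a few children can do (illustration).** Suppose two children have a constant score of 4 unrelated to eye pain. If both are in one arm, they raise its mean by:
- 2 × 4 / 20 = 0.4 in the insert arm
- 2 × 4 / 10 = 0.8 in the control arm
- 2 × 4 / 5 = 1.6 in a control procedure group

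This is an unfavourable draw. Both fall in control with probability 5/15 × 4/14 = 9.5% if they are in the same procedure group, or 1/3 × 1/3 = 11% if in different ones. In expectation they add 8/30 = 0.27 to each arm's mean.

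**Step 2: chance imbalance.** Let X ~ Bin(n₁, p) and Y ~ Bin(n₂, p), independent. The table gives P(|X/n₁ − Y/n₂| ≥ 0.20).

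| Share p | 20 vs 10 | 10 vs 5 |
|---|---|---|
| 0.1 | 12.6% | 35.1% |
| 0.2 | 25.7% | 49.4% |
| 0.3 | 32.6% | 55.5% |
| 0.5 | 36.9% | 59.1% |

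In a 5-child arm one child is already 1/5 = 20 points, so the last column partly reflects coarse counts.

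**Step 3: precision of the arm difference.**
- Raw: SE = SD × √(1/n₁ + 1/n₂). Overall √(1/20 + 1/10) = 0.387 SD, normal 95% half-width 1.96 × 0.387 = 0.76 SD. Within a procedure group √(1/10 + 1/5) = 0.548 SD, half-width 1.07 SD.
- Adjusted for screening: variance × (1 − ρ²).
- Change from screening: variance × 2(1 − ρ).

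| ρ | Raw SE | Adjusted SE | Change SE |
|---|---|---|---|
| 0.2 | 0.387 | 0.379 | 0.490 |
| 0.5 | 0.387 | 0.335 | 0.387 |
| 0.8 | 0.387 | 0.232 | 0.245 |

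These are overall SEs in SD units; the small loss from estimating the slope is ignored. Adjustment cuts the variance by 4%, 25% and 64%. A change score is worse than the raw score below ρ = 0.5, equal at 0.5 and better above it.

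**Step 4: check with zero-heavy scores.** I simulated 20 vs 10 children with no treatment effect. At screening 30% scored 1 to 4 and the rest 0. Each score was carried to day 45 with a set probability and otherwise redrawn, and a random 10% of children gained 1 to 3 points. The SD of the arm difference (raw, change, adjusted) was 0.559, 0.567, 0.510 with carry-over 0.5, and 0.564, 0.406, 0.395 with carry-over 0.8. Adjustment was best in both cases; change alone gave no gain in the first.

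**The case against.** The case against has real weight.

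- **Safeguards exist.** Appendix 10.3 states "BCVA and FLACC will occur prior to other visit assessments" and "The FLACC assessment will be performed by masked site personnel". This limits distress caused by the examination and rater bias. Section 4.1.2 also excludes children who cannot engage in acuity testing. These points stand, but they do not remove distress present on arrival.
- **A reader might infer that the screening score measures fear directly.** The documents do not support that. Only ocular pain is excluded, so other pain could raise the score. Screening may be 30 days before the procedure, and behaviour may change after surgery. The score is an indirect indicator.
- **A reader might infer that the score goes unused altogether.** That is too strong: Section 8.1.1 could cover a baseline summary. What is missing is any stated use in the pain analysis.
- **A reader might infer that the arm comparison is biased.** It is not. Randomisation balances such behaviour in expectation, and this is a descriptive feasibility study with no planned test.
- **The score may carry no information.** FLACC is the only pain assessment scheduled at screening. If the exclusion were applied as FLACC above 0, every enrolled child would start at 0 and adjustment would do nothing. A reader might go on to infer that frightened, pain-free children are being screened out. The documents do not say how the exclusion is judged, so this is missing detail, not a demonstrated error.

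The feasibility label does not dispose of the point. With no test planned, the descriptive summaries are the result, so they need to be interpretable.

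**Conclusion.** The point holds as a gap in the analysis plan. The primary pain outcome is the unadjusted day-45 FLACC score, and no use of the already collected screening score is specified for it, although BCVA is analysed against its baseline. The cost is harder interpretation of absolute scores, avoidable noise, and chance imbalance that can pass for a pain difference. There is no systematic bias between arms.

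The size depends on quantities the documents do not give. Under the assumed ranges, the chance of a 20-point imbalance is 13% to 37% overall and 35% to 59% within a procedure group, and the variance recoverable by adjustment is 4% to 64%. It falls to nothing if nearly all screening scores are 0. That FLACC picks up behaviour unrelated to eye pain is inferred from its items; its frequency in this trial is unknown.

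**What to change.** In the primary endpoint and Section 8:

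- Keep the raw FLACC score at each visit as the reported outcome.
- Report beside it, by arm and procedure group, the distribution of screening FLACC.
- Present the overall day-45 arm difference adjusted for screening FLACC next to the unadjusted one. Groups of 10 and 5 are better left to description.
- Show change from screening as a descriptive column only.

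Do not replace the raw score with a change score, which loses precision when the correlation is below 0.5. Do not define pain resolution solely as a return to the screening score: a child who scored 4 at screening for other reasons and later scores 4 from real pain would be counted as resolved.

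The cost is a few sentences and slightly more analysis work. No extra data, visits or children are needed. If nearly all screening scores are 0 there is no gain, but the table would show that.

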## 2. STUDY OBJECTIVES

### 2.1 Primary Objective

To determine if pediatric retinal patients would benefit from the placement of the 0.4 mg sustained release Dexamethasone intracanalicular insert (DEXTENZA) in the inferonasal lacrimal system during surgery in the surgical/treated eye compared to topical ocular drop therapy to manage post-operative pain (measured with Face, Legs, Activity, Cry Consolability (FLACC) Behavioral Pain Rating Scale). Pain will be measured at each visit with final outcome determined by the FLACC Behavioral Pain Rating Scalescore on day 45.

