### **4. SELECTION, WITHDRAWAL, AND REPLACEMENT OF PATIENTS**

#### **4.1 Study Population**

The study aims to enroll 30 pediatric patients undergoing routine retinal surgery or laser treatment under anesthesia. Patients in each treatment group (surgery or laser) will be randomized 2:1 at the time of surgery/laser to receive either:

- 3) Treatment Arm: Dextenza insert intraoperatively for perioperative ocular inflammation and pain. These patients will not be prescribed topical steroid drops post-operatively, or
- 4) Control Arm: Prednisolone forte 1% steroid drop taper for 28 days post-operatively to treat perioperative ocular inflammation and pain; drops four times per day (QID) on days 0-7, three times per day (TID) on days 7-14, twice per day (BID) on days 14-21 and once per day (QD) on days 21-28.

Each treatment group (surgery or laser) will include 15 patients total, 10 receiving Dextenza and 5 receiving the control drug. Drops for dilation and antibiotic coverage will be used as clinically indicated in all groups throughout the study period. Follow up will occur at post-op day 1, 7, 28/30 and 45 (+/- three days for all post-operative timepoints).

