## **4.2 Treatment Logistics and Accountability**

### **4.2.1 Packaging, Labeling, and Storage**

Intracanalicular dexamethasone insert must be stored in a secure area accessible only to the Investigator and their designee(s) and refrigerated and stored between 2° C and 8° C. Intracanalicular dexamethasone insert contains 0.4 mg dexamethasone and is designed to provide a sustained and tapered release of therapeutic levels of dexamethasone to the ocular surface for up to 30 days for the reduction of post-surgical inflammation and pain associated with ocular surgery. Dexamethasone is an anti-inflammatory 9-fluoro-glucocorticoid (also termed a glucocorticoid agonist) and is the active ingredient found in

MAXIDEX® 0.1% (dexamethasone ophthalmic suspension), which contains approximately 50 µg of dexamethasone per drop.

Study inserts will be supplied by Ocular Therapeutix in a sealed foil pouch containing one intracanalicular dexamethasone insert in a foam carrier.

Study inserts will be shipped to the site via overnight shipping using cold packs to maintain a temperature of 2° to 8° C. The Investigator, or an approved representative (e.g. pharmacist), will ensure that all study drug inserts are stored in a secured area, under recommended storage conditions and in accordance with applicable regulatory requirements. The shipping box is to be opened and stored immediately at the site in a refrigerator intended for investigational products at a temperature of 2° to 8°C.

When the insert is removed from the refrigerator, it should be visually inspected. Exposure of the insert to temperatures outside these limits is not recommended. Records of actual storage conditions (i.e. temperature log) at the study site must be maintained; and must include a record of the dates, when the refrigerator was checked, the initials of person checking, and the temperature.

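### The primary FLACC score is read at Day 45, nominally 15 to 17 days after either treatment ends, so it is very unlikely to be informative about post-operative pain control

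*Combined protocol and SAP*

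**What the plan says.** The primary objective (section 2.1) is whether the insert helps children "compared to topical ocular drop therapy to manage post-operative pain". The deciding reading is fixed in two places that agree:

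- Synopsis, Primary Endpoint: "Pain will be measured at each visit with final outcome determined by the FLACC Pain Rating Scale score on day 45 (final visit".
- Section 2.1: "Pain will be measured at each visit with final outcome determined by the FLACC Behavioral Pain Rating Scalescore on day 45".

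Treatment ends well before that visit. Control children receive "Prednisolone forte 1% steroid drop taper for 28 days post-operatively to treat perioperative ocular inflammation and pain" (section 4.1), with the last step "once per day (QD) on days 21-28". The insert, placed on Day 0, is described as giving "therapeutic levels of dexamethasone to the ocular surface for up to 30 days" (section 4.2.1).

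FLACC is also scheduled at screening and at Days 1, 7 and 28 in both arms (section 5.1, Tables 1 and 2; section 5.2.1). Masked site staff score it (section 10.3). All post-operative visits carry a window of 3 days either side. Resolution of pain by FLACC is a secondary objective (section 2.2), with no visit or threshold named. Section 8.1 calls the trial a feasibility study that is not powered for differences between arms. It plans descriptive statistics by arm, overall and by procedure group. No section explains why Day 45 was chosen.

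**The concern.** The question is about pain after surgery while one of two steroid treatments is being given. The reading that answers it comes after both have nominally stopped. FLACC has a floor at 0. If most children have recovered by Day 45, both arms will sit near that floor whatever happened in the first weeks, and the primary result will look the same for an insert that controlled early pain better, equally or worse than drops.

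The informative readings are collected but do not decide the outcome. If the Day 45 scores turn out flat, the natural response is to turn to Day 1 or Day 7. In an open-label trial, making that switch after results by arm are known would be post hoc selection of the endpoint.

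**Working it through.** **Plan's own figures.** Allocation is 2:1. For 30 children that is 30 × 2/3 = 20 insert and 30 × 1/3 = 10 control. For each procedure group of 15 it is 10 and 5. Both agree with section 4.1. The plan gives no expected FLACC score, standard deviation, pain rate or effect size, so there is no stated figure for Day 45 to reproduce.

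**Gap between end of treatment and the primary reading.** The Day 45 window runs from Day 42 to Day 48.

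| Arm | Treatment ends | Day 42 | Day 45 | Day 48 |
|---|---|---|---|---|
| Drops (section 4.1) | Day 28 | 14 days | 17 days | 20 days |
| Insert (section 4.2.1) | Day 30 at the latest | 12 days | 15 days | 18 days |

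**Floor, for illustration.** Let p be the share of children still scoring above 0 at Day 45. The values of p are assumptions. Children are taken as independent, and p as the same in both arms.

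- All 10 controls score 0: (1 − p)^10 = 0.98^10 = 0.817, 0.95^10 = 0.599, 0.90^10 = 0.349. When this happens the insert arm cannot score lower than control, so no benefit can appear.
- All 20 insert children score 0: (1 − p)^20 = 0.668, 0.358, 0.122. When this happens the insert arm cannot score higher than control.
- All 30 score 0: (1 − p)^30 = 0.545, 0.215, 0.042.

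**How much residual pain would be needed.** The plan specifies no test, so this is only a yardstick. Suppose no insert child has pain at Day 45. By two-sided Fisher exact test, 0/20 against 2/10 gives p = 45/435 = 0.103, and 0/20 against 3/10 gives p = 120/4060 = 0.030. At least 3 of 10 controls would need pain. If the true control rate is 5%, 10% or 20%, the binomial chance of 3 or more is 1.2%, 7.0% or 32%.

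**Early against late reading.** Assume the insert halves the share of children with any pain (20 against 10, Fisher exact, two-sided 5%).

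| Control share with pain (assumed) | Power |
|---|---|
| 2%, 5%, 10% (late, near the floor) | 0.1%, 0.7%, 3.0% |
| 40%, 60%, 80% (early) | 18%, 28%, 44% |

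An early reading leaves room for a difference to appear. It does not make 30 children an adequately powered sample, and the plan does not claim that.

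**Windows of the early visits.** Day 1 ± 3 is nominally Day −2 to Day 4, and Day 7 ± 3 is Day 4 to Day 10. As written, a Day 1 reading could nominally precede surgery, and both visits could fall on Day 4.

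**The case against.** The best defence is that this is a feasibility study with descriptive analysis only. It plans no test or margin, and early FLACC is recorded and can be tabulated. Day 45 might also pick up late or rebound pain. Much of this stands: it is not a sample-size error, and no early data are lost. But a descriptive mean is subject to the floor as much as a test is, and the protocol keeps a comparative primary endpoint. The secondary objective on resolution of pain is too loosely defined to take its place. Rebound inflammation is already a separate secondary objective, and a secondary Day 45 reading would still serve it.

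Several stronger readings are tempting, and the documents do not support them:

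- *Day 45 cannot show a benefit.* No expected scores are given, so the floor is inferred. At the assumed 10%, at least one control scores above 0 in 1 − 0.349 = 65% of trials.
- *Both treatments always ended more than two weeks earlier.* This is true at nominal days. At Day 42 the gaps are 14 and 12 days. Off treatment is also only nominal, since section 5.3 leaves rescue, which may include steroids, to the surgeon, with no rule for scores taken after it.
- *Excluding children with "Ocular pain at the time of screening" (section 4.1.2) creates the floor.* A child without pain before surgery can have pain after it, and the criterion says nothing about how fast that pain resolves.
- *Behavioural items such as "Kicking, or legs drawn up" (section 10.3) push older children's scores to 0.* The scale also scores facial expression and complaints, and no figure in the documents shows lower scores with age.
- *A numerical self-rating can be added because every child must manage acuity testing.* HOTV is a matching task for pre-literate children (sections 5.2.1 and 10.2), so it does not show that a child can use such a rating.
- *A null result will be taken as equivalence.* The plan makes no equivalence claim, so this would be a guess about readers.

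**Conclusion.** The concern holds as one of endpoint timing. The deciding FLACC score falls nominally 17 days after the drop taper and 15 days after the insert's stated release period (14 to 20 and 12 to 18 days across the window), and no reason is given. It is very unlikely to be informative about how well either treatment manages post-operative pain.

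The dates are read directly from the protocol. The floor is an inference from those dates and from a scale bounded at 0. The 82%, 60% and 35% chances that all controls score 0 rest on assumed residual rates of 2%, 5% and 10% and illustrate its possible size; they are not estimates. The fault lies in which visit decides the primary outcome, and data collection and sample size are not at issue.

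**What to change.** In the Synopsis and section 2.1, pre-specify as primary a summary of the masked FLACC totals already scheduled during treatment, for example each child's mean over the Day 1 and Day 7 visits. A repeated-measures summary or area under the curve would also serve, provided one is named.

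- Restrict the Day 1 window to post-operative days before Day 4, where the Day 7 window opens.
- State how the summary treats a score recorded after rescue.
- Keep Day 28 and Day 45 as secondary readings, with Day 45 labelled as off-treatment or rebound.
- Report by arm, overall and by procedure group, descriptively, as section 8.1 already plans.

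The cost is amendment wording and a narrower Day 1 window, with no new visit or assessment. The downside is that Day 45 becomes secondary. Because the trial is open-label, the change must be made and dated before outcome data by arm are examined; after that it could not be presented as pre-specified.
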